Aim : To compare 2 combination DMARD therapies (MTX+SSZ+HCQ versus MTX+LEF+HCQ) in patient with early RA who have failed MTX monotherapy

Objectives :

1. To assess safety and efficacy of MTX+LEF+HCQ based combination DMARD therapy in patients with early RA failing MTX monotherapy
2. To assess safety and efficacy of MTX+SSZ+HCQ based combination DMARD therapy in patients with early RA failing MTX monotherapy
3. To compare the safety and efficacy profile of 2 combination DMARD therapy (MTX+LEF+HCQ and MTX+SSZ+HCQ)

Methodology

- A. Study design/type:** Randomized parallel group non-inferiority trial, pragmatic design
- B. Study participants:** Humans

For Participants

- a. Inclusion criteria :

Age >18 years satisfying ACR-EULAR criteria for RA

1. Polyarthritis (>4 joints)
2. Disease duration of less than 2 years
3. Patients with moderate to severe disease activity (DAS28 \geq 3.2)
4. Patients who have failed to respond to initial Methotrexate monotherapy

b. Exclusion criteria :

1. End stage disease (deformed fixed joints)
2. Patients with vasculitis, extra-articular features like interstitial lung disease
3. Contraindications to DMARD therapy (Chronic Alcoholism, Chronic liver disease, Evidence of acute/chronic infection, Chronic kidney disease, Patients with leucopenia ($<3.0 \times 10^9/l$), thrombocytopenia ($<150 \times 10^9/l$), AST/ALT $>2 \times$ upper normal value and creatinine clearance <30 ml/minute)
4. Pregnant, lactating women ; patients (both men and women) of reproductive age group unwilling for contraceptive use who have not completed the family
5. Patients unable to come for regular follow up

c. **Number of groups to be studied, their names and definitions:**

Group 1: MTX+LEF+HCQ

Group 2: MTX+SSZ+HCQ

C. Sampling

a. Sampling Population : Patients >18 years of age diagnosed with RA, attending OPD services of the Department of Clinical Immunology

b. Sample size calculation : (calculated for non inferiority trial)

Sample size has been estimated as 70 patients in each group using the N master software considering success rate as 75 % in both groups (calculated from FIN-RACo trial group, Lancet 1999 (13)) and non inferiority limit as 20% with 5 % alpha error ,statistical power of 80 % and dropout rate as 20%

c. Sampling technique: block randomization

D. Randomization details: block of 10, 1:1 random allocation.

E. Study Procedure

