A. Selection of participants: All consecutive patients of RA attending the OPD services of the department of Clinical Immunology will be included to reach a minimum sample size of in each group.

[figure not shown]
B. Patients will be assessed for eligibility and will be started on Methotrexate monotherapy initially and then only patients, who have moderate to severe disease activity inspite of 12 weeks of Methotrexate monotherapy, will be randomized to either of the 2 groups of DMARDs.

C. Allocation to groups:

Allocation concealment will be done by : Sequentially numbered, opaque, sealed envelopes (SNOSE) method

Group 1: MTX+LEF+HCQ

Group 2: MTX+SSZ+HCQ

F. Data Collection method including settings and periodicity: Patients aged above 18 years diagnosed as RA according to the 2010ACR-EULAR criteria will be screened and evaluated for inclusion in the study. The patients will be examined every 2 week interval during DMARD dose escalation & then every month for next 6 weeks of MTX and for 24 weeks for either groups.

a. Clinical evaluation:

- i. Adverse drug reactions (ADRs) – each visit
- ii. IHAQ, DAS28 - once at baseline and then at 12 weeks of MTX monotherapy and then at the end of 24 weeks treatment with either of Group 1 or group 2 drug.

b. Laboratory:

- i. Routine CBC/RFT/LFT: every 2 week interval during dose escalation & then every month for 12 weeks after starting the drug
- ii. ESR & hsCRP for disease activity evaluation: every month.
- iii. **USG** wrist, hand and feet (US-7 score)- at baseline and at 12 weeks of Group 1 or group 2 drug

G. List of variables and their measurement methods with standardization techniques:

a. (i) Independent variables

Socio-demographic profile:

- Age
- Gender

b. Outcome Variables:

Disease-related parameters –

Primary outcome measures:

- a. Disease activity (state) - DAS28

Secondary outcome measures:

- a. Functional ability – iHAQ
- b. Mean changes over time in:
 - i. Inflammatory parameters: ESR, hs-CRP
 - ii. Disease activity as per US-7 score
- c. Adverse drug reactions

Primary endpoint:

Proportion of patients in both groups achieving good response according to European League Against Rheumatism (EULAR) response criteria at the end of 12 weeks of combination therapy

Secondary endpoint:

1. Change in functional ability (Indian Health Assessment Questionnaire; iHAQ) at the end of 12 weeks of combination therapy
2. disease activity by US7 score at 12 weeks

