The trial is designed as a non-inferiority pragmatic trial. The assessment will be done in unblinded fashion by the researcher. Arbitrarily considering EULAR good response rate (primary endpoint) of 75% with SSZ based triple regimen (tREACH and TICORA study) and non-inferiority margin of $\Delta = (-20\%)$ for LEF, a sample size of 140 (70 in each group) was determined using nMaster sample size calculator (version 2 software) using 2-sided confidence levels (CI) of 95%, power of 80% and dropout rate of 20%.

Data will be analyzed using SPSS (IBM pasw statistics, version 19.0) for windows. For quantitative data [DAS28ESR, iHAQ], normality of distribution will be checked by Shapiro-Wilks W test. Continuous data was presented as median and interquartile range (IQR₂₅₋₇₅) / mean with SD as appropriate. Mann-Whitney U test / Students t test will be used for comparison between median/ mean of 2 groups respectively. Qualitative or categorical variables (such as EULAR good response) will be described as proportions and will be tested using Chi-square. Odds ratio (OR) – odds of achieving the outcome (treatment response) in patients exposed to LEF in comparison to patients not exposed to LEF (SSZ group) along with 95% confidence interval and p-value will be used to study the statistically significant difference in treatment outcome between 2 groups. P-value of <0.05 was considered as significant.

The primary endpoint will be analyzed by both intention-to-treat (ITT) and per-protocol (PP) analysis. The rest of the parameters will be analyzed by ITT analysis only. Patients who do not complete the study, the last observation will be taken as their outcome for ITT analysis. For missing data, the last available readings will be carried forward in case of patients who are not available for the endpoint assessment. Non-inferiority testing will be done by using a 95% confidence interval (CI) of the difference between the proportions of patients achieving the primary endpoint between 2 groups. Extension of CONSORT 2010 statement will be used for reporting of non-inferiority of the LEF group.

DATA COLLECTION PROFORMA

CODE NO:

Date of enrollment:

Name/ age/ sex/ CCR no :

Contact number

Disease duration:

Co-morbid conditions (with duration):

Personal history (habits/addictions):

Treatment history:

Family history:

Baseline Investigations:

RF:

HIV:

HBsAg:

HCV:

Anti-CCP:

Mantoux test:

Drug

Dose

since when

Side effects

1

2

3

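### The primary non-inferiority interval leaves out DAS28 at randomisation, which every randomised patient has: a missed gain in precision of uncertain size

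*Combined protocol and SAP*

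**What the plan says.** The primary endpoint is binary: "Proportion of patients in both groups achieving good response according to European League Against Rheumatism (EULAR) response criteria", assessed after 12 weeks of combination therapy (protocol, Primary endpoint). The third paragraph of the SAP gives the deciding analysis: "Non-inferiority testing will be done by using a 95% confidence interval (CI) of the difference between the proportions of patients achieving the primary endpoint". The SAP's second paragraph adds a chi-square test and an odds ratio for the same endpoint. None of these names a covariate, a regression model or a stratified analysis.

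Section D, Randomization details, reads "block of 10, 1:1 random allocation" and names no stratification factor.

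Section F.a.ii schedules DAS28 "once at baseline and then at 12 weeks of MTX monotherapy". The second of these is the point of randomisation. Because patients are randomised only if disease activity is still moderate to severe at that visit, the value must exist for every randomised patient.

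**The concern.** Response is graded from DAS28, and DAS28 at randomisation is an earlier reading of the same measure. It is therefore the natural candidate to explain part of the variation in who responds. Neither the randomisation nor the primary analysis uses it.

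A standardised risk difference would test the same margin on the same scale with an interval that is usually as narrow or narrower. That matters because the sample size has no slack under the interval the SAP plans to use. Assessment is also unblinded (SAP, first paragraph), so an adjustment fixed in advance is worth more than one chosen after the data are seen.

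**Working it through.** **Inputs from the documents.** Response 75% in both arms, margin 20 points, power 80%, dropout 20%, 70 per group (protocol, Sample size calculation; SAP, first paragraph). The protocol gives alpha as 5% without saying whether it is one- or two-sided. The SAP uses a two-sided 95% interval, which is one-sided 2.5% for non-inferiority.

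**Reproducing the 70.** With unpooled variance, n = 2 × 0.75 × 0.25 × (z_α + z_β)² / 0.20² = 0.375 × (z_α + z_β)² / 0.04.
- One-sided 5%: n = 57.96. Multiplying by 1.2 gives 69.6, so 70, which matches. Dividing by 0.8 gives 72.5, which does not.
- One-sided 2.5%, as in the SAP: n = 73.6, so 74 evaluable per group. With dropout this is 89 (74 × 1.2 = 88.8) or 93 (74 / 0.8 = 92.5). Neither matches.

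**Raw power under the SAP's interval.** Power = Φ(0.20/SE − 1.96), with SE = √(0.375/n).
- 70 per group: SE = 0.0732; 0.20/0.0732 − 1.96 = 0.77; power 78.0%.
- 56 per group (70 × 0.8): SE = 0.0818; 0.20/0.0818 − 1.96 = 0.48; power 68.6%.

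**Gain from adjustment.** The documents give nothing from which to derive it. Assumptions: DAS28 at randomisation with mean 4.5 to 5.5 and SD 1, truncated at the entry threshold of 3.2; good response taken as week-12 DAS28 of 3.2 or less with a fall above 1.2 from randomisation; about 75% responders. Simulated trials with 70 per group, adjusting for DAS28 and DAS28 squared, give the standard-error ratios and simulated power below. The formula columns put each ratio k into Φ(0.20/(k × SE) − 1.96). The last column assumes that the same ratios hold at 56 per group.

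| Correlation of DAS28 at randomisation with week 12 | Adjusted/raw SE | Simulated power, 70 per group | Formula, 70 per group | Formula, 56 per group |
|---|---|---|---|---|
| 0.3 | 0.99–1.00 | about 78–80% | 78.0–78.8% | 68.6–69.5% |
| 0.5 | 0.94–0.99 | about 80–82% | 78.8–82.8% | 69.5–73.9% |
| 0.7 | 0.84–0.92 | about 84–90% | 84.4–90.2% | 75.7–82.9% |

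Simulated raw power was about 78–80%, so differences of a point or two are noise. In equivalent patients (1/k² − 1), the gain is 0–2%, 2–13% and 18–42%.

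**What 80% power needs.** If DAS28 explains a share R² of the response variance, the variance falls by the factor 1 − R². The requirement is R² = 1 − n × 0.04 / (0.375 × 7.85), where 7.85 = (1.96 + 0.84)² before rounding. This gives 0.05 at 70 per group (SE ratio 0.975) and 0.24 at 56 per group (SE ratio 0.87).

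**Why a squared term.** Under the assumed rule a low entry value must still fall far enough and a high one must still reach the target, so the relation need not be monotone. At mean 5.0, SD 1 and correlation 0.2, a straight-line term explains essentially none of the variance and a flexible one 0.02. At correlation 0.6 and 75% response the figures are 0.15 and 0.18.

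**Chance imbalance.** The standardised difference in mean DAS28 has standard error √(2/70) = 0.17, so a 95% range of ±0.33. The resulting shift in the risk difference has SD √R² × 0.0732: 1.0 point at R² = 0.02 and 3.3 points at R² = 0.20.

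**The case against.** The strongest reply is that nothing here is wrong. In a randomised trial the raw interval is valid, and chance imbalance in DAS28 is part of the sampling variation it already covers. In simulation at a true difference of −20 points, one-sided error was 2.1–2.9% for both the raw and the adjusted analysis. A reader might infer that an uncorrected imbalance biases the result; the plan does not support that. An imbalance of a third of an SD is the edge of the 95% range, and the typical shift is 1.0–3.3 points against a 20-point margin. All of this stands.

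A reader might also infer that DAS28 at randomisation strongly decides who can respond. The documents do not support that either. They cite the EULAR criteria without thresholds, do not say whether the pre-MTX or the randomisation value is the reference, and give no DAS28 distribution or correlation. At correlation 0.3 the gain is close to nil. Only a plausible association can be claimed.

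Lastly, a raw difference is simpler to explain, and adjustment is not quite free. With no association and 56 per group, simulated power was 68.8% raw and 67.5% adjusted, a difference small enough that it may be noise.

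What remains is that a covariate available for every patient, closely tied to the endpoint, goes unused when raw power is already below its stated target.

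**Conclusion.** The point holds as a missed gain in precision. It is not a bias, and the planned interval does not have to be replaced for the trial to be valid. With all 70 per group, prespecified adjustment would bring power from about 78% to somewhere between 78% and 90%, according to a correlation the documents do not give. About 5% of response variance explained would be enough to reach 80%.

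It should not be read as a cure for the trial's power. With 56 per group, 80% requires R² of about 0.24, which the assumed scenarios reach only in part of the range at correlation 0.7. That shortfall comes from the sample size matching a one-sided 5% test while the analysis uses a two-sided 95% interval, and from the dropout inflation. It is a separate matter to settle.

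**What to change.** In the third paragraph of the SAP, prespecify as the primary estimate the LEF minus SSZ risk difference standardised over DAS28 at randomisation:

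- Name the covariate as the DAS28 measured at the end of 12 weeks of MTX, to distinguish it from the pre-MTX value, and state which of the two is the reference for EULAR response.
- Fit a logistic model with arm, DAS28 and DAS28 squared. Average the predicted risks over all patients under each arm and take the difference, with a robust, delta-method or bootstrap 95% interval (name one).
- Compare the lower limit with −20 points in both ITT and PP.
- Report the raw difference and its 95% interval as a sensitivity analysis.

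An adjusted odds ratio would not serve, because the margin is on the risk-difference scale.

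The cost is a few lines of SAP text, a short extra computation (check that the named SPSS version can produce it, or name another program) and a slightly less transparent estimate. No new data are needed. If the correlation is low there is essentially no gain and at most a trivial loss.

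### Week-12 DAS28ESR should be reported as a mean difference with a 95% CI, as support for the responder test; the planned t or Mann-Whitney p-value cannot inform non-inferiority

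*Combined protocol and SAP*

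**What the plan says.** - **Outcome measure.** Protocol section G gives the primary outcome measure as "Disease activity (state) - DAS28".
- **Primary endpoint.** The protocol then defines the endpoint as "Proportion of patients in both groups achieving good response according to European League Against Rheumatism (EULAR) response criteria at the end of 12 weeks" on the allocated regimen.
- **Non-inferiority test.** SAP, third paragraph: "Non-inferiority testing will be done by using a 95% confidence interval (CI) of the difference between the proportions of patients achieving the primary endpoint". The SAP's first paragraph sets the margin at -20 points for leflunomide (LEF), with a two-sided 95% confidence level.
- **Continuous DAS28.** SAP, second paragraph, treats DAS28ESR as quantitative: "Mann-Whitney U test / Students t test will be used for comparison between median/ mean of 2 groups respectively". Significance is set at 0.05. Intervals are planned for the odds ratio and for the difference in proportions, but not for a difference in DAS28.
- **Analysis sets.** The primary endpoint is analysed by ITT and per protocol (PP). Everything else is confined to ITT, with the last observation carried forward.
- **Secondary endpoints.** The list covers iHAQ, US7, safety and week-24 good response. DAS28 as a score is not on it.
- **Data.** The data collection proforma has DAS28 columns at baseline and every 4 weeks to week 24. The protocol's section on treatment response reassesses disease activity at weeks 12 and 24 after allocation.

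**The concern.** A t or Mann-Whitney test asks whether the two groups differ. A non-inferiority trial asks how much worse the new regimen could be. A p-value without an interval does not answer that: a large p-value may mean that the groups are close, or only that the data are imprecise. As planned, the comparison of the score on which the primary endpoint is built adds nothing to the trial's question.

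This would matter little if the responder comparison had precision to spare, but it does not. If its interval crosses the margin, readers will look to DAS28 for help in interpreting the result and will find only a p-value, in the ITT set alone.

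**Working it through.** **1. Inputs from the documents.** Good response 75% in both groups (protocol, sample size calculation: "considering success rate as 75 % in both groups"); margin 20 points; 70 per group; dropout 20%, which leaves 70 x 0.8 = 56. ITT with values carried forward may keep up to 70 per group; PP is nearer 56.

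**2. The plan's own figure.** n per group = (z_alpha + z_beta)^2 x 2 x 0.75 x 0.25 / 0.20^2.
- One-sided 5%: (1.645 + 0.842)^2 x 0.375 / 0.04 = 58, and 58 x 1.2 = 70. This reproduces the stated 70.
- One-sided 2.5%, which is what the SAP's two-sided 95% CI implies: (1.960 + 0.842)^2 x 0.375 / 0.04 = 74 before dropout.

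**3. Precision of the planned primary test** (two-sided 95% CI, true difference zero). SE = sqrt(0.375/n); power = Phi(0.20/SE - 1.96).

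| Analysed per group | SE | CI half-width | Power | Fails to conclude |
|---|---|---|---|---|
| 70 | 0.0732 | 14.3 points | 78.0% | 22% |
| 56 | 0.0818 | 16.0 points | 68.6% | 31% |

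**4. What the full scale could add.** The documents give no DAS28 SD, distribution, baseline correlation or margin, so this step rests on assumptions: normal DAS28, equal SDs, and good response treated as a single cut. A fall from 75% to 55% is then a shift of z(0.75) - z(0.55) = 0.674 - 0.126 = 0.549 SD.
- Mean difference against 0.549 SD: SE = sqrt(2/n) SD; power = Phi(0.549/sqrt(2/n) - 1.96) = 90.1% (n=70) and 82.7% (n=56). The gain is 12.1 and 14.2 points (from unrounded values).
- Good-response difference estimated from the normal model, against the existing -20 points: variance per group = phi(z)^2 (1 + z^2/2)/n with z = 0.674; power 91.9% and 85.2%. The gain is 91.9 - 78.0 = 13.9 and 85.2 - 68.6 = 16.6 points. The half-width at n=70 falls from 14.3 to 11.7 points.

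**5. How far the gain depends on the assumptions.** Pairs are for n=70 and n=56.

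| Change of assumption | Effect on power compared with the responder CI |
|---|---|
| Mann-Whitney efficiency (0.955), mapped margin | +10.7, +12.4 |
| Response as a level-plus-change rule (assumed baseline mean 4.5 to 5.5, correlation 0 to 0.5) | about +8 to +17 overall |
| True response 85%, mean difference | +5.9, +8.9 |
| True response 60%, mean difference | +17.5, +18.5 |
| One-sided 5%, mean difference | +8.4, +10.8 |
| Skewed (gamma) data, model-based estimate | 86.0 - 78.0 = +8.0; 78.7 - 68.6 = +10.1 |
| Fixed DAS28 margin 0.6, assumed SD 1.2 | +6.1, +6.8 |
| Fixed DAS28 margin 0.5, assumed SD 1.2 | -8.7, -8.9 |

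**6. Error rate of the model-based estimate.** Simulation of 40,000 trials per setting, with a separate SD in each group and true rates of 55% v 75%. One-sided error was 2.5% and 2.4% for normal data, 6.6% and 5.9% for heavy-tailed t(5) data, and 1.7% and 1.9% for skewed data. The ordinary CI of proportions stayed between 2.3% and 2.7% throughout.

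**The case against.** The strongest reply is that nothing here is an error. A responder endpoint is a legitimate choice, the sample size and margin were built on it, and no citation is needed to justify it. DAS28 is not overlooked either: the protocol names it as the outcome measure and the SAP lists it for quantitative analysis. All of this stands.

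A reader might be tempted by four stronger conclusions, which the documents do not support.

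- **That the trial forfeits 12 to 17 points of power.** That range needs the normal, single-cut model and a margin mapped from the 20 points, none of which is in the documents. With the responder test kept as primary, the power of the trial's conclusion does not change at all. The benefit is a more informative supportive estimate.
- **That an inconclusive primary result is likely.** By the calculation above it happens in 22% to 31% of trials of equal regimens. That is a real risk, but not the expected outcome.
- **That the SAP means to read a non-significant DAS28 test as non-inferiority.** It says nothing of the kind. It ties non-inferiority to the difference in proportions and commits to the CONSORT extension for such trials. A short disclaimer is a precaution, not a correction.
- **That a continuous or model-based analysis should replace the responder test.** The model-based error rate reaches about 6.6% with heavy tails, and a strict DAS28 margin would give less power than the responder CI.

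What survives is narrower: the planned DAS28 comparison has no interval, so it cannot speak to the question that the trial asks.

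**Conclusion.** The point holds as a low-cost improvement, not as a fault in the primary analysis. The wording of the SAP is enough to show that the DAS28ESR comparison is uninformative for non-inferiority; no assumption is needed for that. The case for acting rests on the 22% to 31% chance of an inconclusive primary result under equal regimens, which uses only the SAP's inputs and a normal approximation.

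The size of any gain in precision is not established. It is about 12 to 17 points of power under the assumptions in step 4, about 8 to 10 with the skewed data simulated, and negative if a stricter DAS28 margin is chosen. The recommendation does not depend on that figure.

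**What to change.** Leave the primary endpoint, the -20 point margin and the CI of proportions unchanged. In the SAP:

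1. List week-12 DAS28ESR as a secondary endpoint. Report the LEF minus sulfasalazine mean difference with a two-sided 95% CI in place of the bare p-value.
2. Do this in both the ITT and PP sets. The sentence that confines all non-primary parameters to ITT must be amended to allow it.
3. If the data are clearly non-normal, give a bootstrap CI or the location shift that goes with the Mann-Whitney test.
4. A DAS28 margin is optional. If one is used, fix and justify it in DAS28 units before the data are seen, not as a multiple of the observed SD.
5. Optionally, pre-specify a model-based estimate of the same good-response difference against the existing -20 points, with a bootstrap 95% CI, labelled supportive.
6. State that neither analysis can rescue a failed primary test, and that a non-significant DAS28 test is not evidence of non-inferiority.
7. Add week 12 of combination therapy to the DAS28 timing in protocol section F. That list omits it, although the primary endpoint, the treatment-response section and the proforma all require it.

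The cost is SAP wording and a little extra analysis of data already planned for collection, with no new patients or visits. The downside is that item 5 relies on a distributional assumption.
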